4 STUDY METHODS

4.1 Overall Study Design and Plan

The study is a multi-center, randomized, surgical trial of women with symptomatic uterovaginal prolapse desiring vaginal surgical treatment. The purpose of this study is to compare a vaginal hysterectomy with native tissue apical repairs with a non-trocar mesh hysteropexy repair. Eligible subjects will be randomized 1:1 to receive either vaginal hysterectomy with native tissue apical repairs or a non-trocar mesh hysteropexy repair for treatment of their uterovaginal prolapse. Each of the participants will be followed until 36 months after the last participant is randomized meaning that participants are expected to be followed for a period of 36 to 60 months to assess treatment outcome.

A study schematic is shown below:

4.2 Study Population

The study population is expected to comprise 180 participants (who were enrolled, consented, and randomized) as defined by the following eligibility criteria:

Inclusion Criteria:

- 1) Women aged 21 or older who have completed child -bearing
- 2) Prolapse beyond the hymen (defined as Ba, Bp, or C > 0 cm)
- Uterine descent into at least the lower half of the vagina (defined as point C> -TVL/2))
- 4) Bulge symptoms as indicated on question 3 of the PFDI-20 form relating to 'sensation of bulging' or 'something falling out'
- 5) Desires vaginal surgical treatment for uterovaginal prolapse
- 6) Available for up to 60 month follow-up
- 7) Amenorrhea for the past 12 months from either menopause or endometrial ablation
- 8) Not pregnant, not at risk for pregnancy or agree to contraception if at risk for pregnancy (only applicable to the rare endometrial ablation patient)
- 9) Eligible for no cervical cancer screening for at least 3 years $\frac{40}{,41}$

Exclusion Criteria:

- 1) Previous synthetic material (placed vaginally or abdominally) to augment POP repair
- 2) Known previous uterosacral or sacrospinous uterine suspension
- 3) Known adverse reaction to synthetic mesh or biological grafts; these complications include but are not limited to erosion, fistula, or abscess
- 4) Chronic pelvic pain
- 5) Pelvic radiation
- 6) Cervical elongation- defined as an expectation that the C point would be Stage 2 or greater postoperatively if a hysteropexy was performed. (Note: cervical shortening or trachelectomy is not an allowed intraoperative procedure within the hysteropexy treatment group).
- 7) Women at increased risk of cervical dysplasia requiring cervical cancer screening more often than every 3 years (e.g. HIV+ status, immunosuppression because of transplant related medications, Diethylstilbestrol (DES) exposure in utero, or previous treatment for cervical intraepithelial neoplasia (CIN)2, CIN3, or cancer)

- 8) Uterine abnormalities (symptomatic uterine fibroids, polyps, endometrial hyperplasia, endometrial cancer, or any uterine disease that precluded prolapse repair with uterine preservation in the opinion of the surgeon
- 9) Indication for ovarian removal (adnexal mass, BRCA 1/2 positivity, family history of ovarian cancer)
- 10) Current condition of amenorrhea caused by exogenous sex steroids or hypothalamic conditions.

4.3 Study Arm Assignment and Randomization

After consent is obtained from the participant and eligibility is determined, the participant will be randomized to one of the two treatment arms using a phone-based randomization system after the participant is in the operating room. The patient will be randomized to one of two apical procedures: either a vaginal hysterectomy with USLS or mesh strap vaginal hysteropexy (UPHOLD procedure). Other native tissue vaginal wall prolapse repairs (e.g. anterior colporrhaphy, posterior colporrhaphy, perineorrhaphy) will be allowed as needed.

Randomization (1:1 to the two treatment arms) will be performed using permuted blocks, with a block size that is known only to the DCC and will be stratified by site.

4.4 Masking and Data Lock

4.4.1 General Masking Procedures

The study surgeon is providing clinical care to enrolled participants, thus masking the surgeon to treatment allocation or participant symptoms is not practical or feasible, other than the allocation concealment prior to surgical randomization. The study surgeon will not be preforming the anatomic outcome assessments. It is our intent that when feasible and ethical, all outcomes assessors and the participant will be masked to the treatment allocation. All participants will be asked to remain masked to their treatment group for the duration of the study, although we recognize that unintentional unmasking by the participant may occur. Current ACOG recommendations allow women age 30 years or older with known recent negative cervical cytology and negative HPV testing to be screened no sooner than 3 years.40 Current US Preventative Services Task Force, American Cancer Society, American Society for Colposcopy and Cervical Pathology, and American Society for Clinical Pathology recommendations allow no screening for age <21, every 3 year screening for ages 21-29, every 5 year screening ages 30-65, and no screening for women older than 65. Therefore, all participants in this study should be able to go 3 years without screening and the overwhelming majority of participants in this study will be >30 and are allowed to have every 5 year screening. Unmasking is permitted for the rare amenorrheic woman with a uterus aged 18-30 eligible for this study who in the opinion of the study surgeon needs screening during the study. We recognize that this masking is for cervical cancer screening and women may still have regular exams. In the event the patient is about to have a pelvic exam or imaging study of her pelvis we will request the patient to remind her provider to not tell her about the status of the absence or presence of her uterus. Participants will be encouraged to see the study team for any gynecologic problems or evaluations during the course of the study. At every 6-month visit the participants will be queried if they are still blinded, and if not, what caused the unblinding and what group they think they are in? This will be done in a manner that reaffirms that blinding is preferred for the duration of the study. After the study is completed (maximum 60 months) participants will be queried as to what randomization arm they think they received and will then be notified of their uterine and mesh status. To minimize biases, subjective and most objective outcomes will be obtained by study nurses or coordinators masked to the procedure. POPQ measures will be obtained by co-investigators or different study nurses who will not be blinded to the surgical procedure because they will either see or not see a

cervix, but would be less biased than the operating surgeon towards over-reporting the anatomic surgical outcome.

Masking	Uterovaginal Prolapse
	Intervention
Participant	Yes
Study coordinator or study nurse	Yes
Telephone interviewer (if applicable)	Yes
Study surgeon	No
Anatomic Evaluator#	No#

to maximize masking, the anatomic evaluator not be the study coordinator or study nurse who should remain masked. The anatomic evaluator should be a Co-investigator, fellow, or other qualified nurse who did not perform the surgery.

4.4.2 Database Lock

Because the primary analyses are scheduled at the point that all study participants have completed their 36-month follow-up at a time that many participants are still in long-term follow-up, database lock will be accomplished in two phases. Because the primary analyses utilize a survival analysis approach, the first lock will include visits through 36 months on all study participants plus those 42-, 48-, 54-, and 60-month visits that occur on or before February 16, 2018. That date was selected in a masked fashion by the protocol team to facilitate efficient closure of appropriate files. Any visit-specific forms that meet these criteria will be locked during the first lock. However, forms that are log-based rather than visit-specific (e.g., protocol deviation form, AE form, and concomitant medication form) will not be locked as those forms will have accumulating data. Rather a snapshot of the data will be taken at some date after February 16, 2018, and any events that occurred prior to that date will be archived in a separate analysis database. The remainder of the study data will be locked and corresponding analyses will be completed once all participants have completed their 60-month follow-up period.

Measure	Base-	Peri-	6	6	12	18	24	30	36	42	48	54	60
	line	ор	wks	mo									
Demographic Info	Х												
Medical History	Х												
Operative and Perioperative review		X											
Postoperative recovery			Х										
POPQ	Х			Х	Х	Х	Х	Х	Х	Х	Х	Х	Х
AE review		Х	Х	Х	Х	Х	Х	Х	Х	Х	Х	Х	Х
Exam for mesh exposure			Х	Х	Х	Х	Х	Х	Х	Х	Х	Х	Х
PFDI – Question 3	Х		Х	Х	Х	Х	Х	Х	Х	Х	Х	Х	Х
Functional Activity Scale	Х		Х	Х	Х	Х	Х		Х		Х		Х
Surgical Pain Scale	Х		Х	Х	Х	Х	Х		Х		Х		Х
PFDI- 20 (includes POPDI -6, CRADI-8, UDI-6)	Х		X	X	X	X	X		X		X		X
PFIQ	Х			Х	Х	Х	Х		Х		Х		Х
PGII				Х	Х	Х	Х		Х		Х		Х
ISI	Х		Х	Х	Х	Х	Х		Х		Х		Х
PISQ-IR	Х			Х	Х	Х	Х		Х		Х		Х
BIS	Х		Х	Х	Х	Х	Х		Х		Х		Х
SF-12	Х			Х	Х	Х	Х		Х		Х		Х

4.5 Study Flow Chart of Assessments and Evaluations

5 ANALYSIS POPULATIONS

Intention to Treat (ITT) Population

The primary analysis population and the population for all secondary analyses will be the modified intention to treat population, which includes all randomized subjects. All subjects will be assigned to the arm to which they were randomized irrespective of treatment received.

Safety (SAF) Population

The safety population will comprise all subjects who received any study treatment grouped by actual treatment received, irrespective of treatment dose received.

6 SAMPLE SIZE DETERMINATION

This study is designed to compare the relative effectiveness of two transvaginal apical suspension strategies for uterovaginal prolapse: a mesh augmented hysteropexy vs. vaginal hysterectomy and uterosacral ligament suspension. Power and sample size calculations were generated to determine the sample size needed to test for treatment difference favoring the mesh augmented strategy (i.e., a superiority trial) across the study arms for a variety of assumptions about effect size and study followup time. For all power analyses, we assumed that failure in both arms follows an exponential survival model and that the native tissue repair has a success rate of 80% at 24 months. This 80% calculation is based on an assumed 85% anatomic success rate for uterosacral ligament suspension (Table 2) and an additional 5% failure rate based on symptom failure. In the only published Uphold series there is a 98 % 12 month anatomic success rate.32 Although no 2-year outcome data are available for the UPHOLD procedure, under an assumption of a constant hazard, the 1-year success rate of 98% yields an estimated 2-year anatomic success rate of 96%; combining this estimate with a similar 5% rate for symptom failure yields a 91% composite (anatomic and symptom) success rate. All analyses also assumed that statistical tests would be conducted with a Type I error rate of 0.05 with no adjustment for multiple comparisons. Sample size estimates assumed that the 2-year success rate in the meshaugmented arm is in the range of 90% to 93% at 24 months (note that this represents a hazard ratio in the range of 0.33 to 0.47 under the assumed exponential survival model), that the enrollment time for the study is 2 years, the loss-to-follow-up on both arms is no more than 5% per year, and the total study duration from last participant enrolled to stopping the study for final analysis is 36 months with one interim analyses for efficacy when the last participant reaches the 24-month follow-up. Table 6 provides estimates of the power for the different assumptions for total sample sizes in the range of 160 to 300 participants.

Total Sample Size	Power as a Function of 2-Year Effect Size—with base 2-Year Success of 80% and 36-Month Follow-up after last enrollment and a 2-year Enrollment Period						
	∆= 0.10 HR=0.472	Δ=0.11 HR=0.423	Δ=0.12 HR=0.374	∆=0.13 HR=0.325			
160	0.87	0.93	0.96	0.99			
180	0.89	0.95	0.98	0.99			
200	0.92	0.96	0.99	>0.99			
220	0.94	0.98	0.99	>0.99			
240	0.96	0.98	0.99	>0.99			
260	0.95	0.99	0.99	>0.99			
280	0.98	0.99	>0.99	>0.99			
300	0.98	0.99	>0.99	>0.99			

Based on these calculations, a total of 180 participants will be randomized at a 1:1 ratio to the two treatment arms. This sample size will provide a power of 0.89 to detect an additive difference of 10% in the 2-year success rate (i.e. a hazard ration 0f 0.472) and a power of 0.99 to detect additive differences of 11% or greater in the 2-year success rate (hazard ratios of 0.423 or less).

7 STATISTICAL / ANALYTICAL ISSUES

7.1 General Rules

All statistical computations will be performed and data summaries will be created using SAS 9.2 or higher. If additional statistical packages are required, these will be discussed in the study report. For summaries of study data, categorical measures will be summarized in tables listing the frequency and the percentage of subjects in each study arm; continuous data will be summarized by presenting mean, standard deviation, median and range; and ordinal data will be summarized by only presenting median and range.

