7.2 Adjustments for Covariates

Indicator variables for the study stratification of site will be included as covariates in most efficacy analyses performed for this study (details in section 9). Additionally, demographic and baseline characteristics for subjects and clinicians will be compared between study arms using analysis of covariance techniques for continuous measures, Mantel-Haenszel mean score test using standardized midrank scores for ordinal measures, and Cochran Mantel-Haenszel chi-square tests for general association for categorical measures. If sample sizes allow, these analyses will control for the study stratification factors. If these analyses suggest that substantial differences exist among arms, the use as covariates of these parameters on which the arms differ will be explored in secondary exploratory analyses of the efficacy data.

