9 EFFICACY ANALYSES

9.1 Overview of Efficacy Analyses Methods

All efficacy analyses will be performed using the ITT population unless otherwise specified. All efficacy variables will be listed by subject within study center and assessment time. The data will be summarized by treatment group.

The primary efficacy outcome measure is a binary measure of treatment failure/success as determined at 6-month time intervals post-intervention, and the primary analytic approach will utilize a survival model to evaluate differences in time to treatment failure between the two treatment arms. Generally, all secondary efficacy variables will be collected longitudinally across this study at six-month. Consequently, secondary analyses will be conducted using appropriate models for these correlated data collected across time. Specifically, continuous outcome variables will be analyzed using linear mixed models and binary outcome variables will be analyzed using robust Poisson regression models with a log link. Most models will include terms for treatment, time, and the treatment by time interaction and for the stratification variables included in the study design (site). Additional details are provided in the specific sections below.

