Duration of post-operative catheterization	Continuous	Time to removal of the catheter post-operatively obtained directly from CRF data.
Urinary functional distress as measured PFDI-SF Urinary Distress Inventory scale at 6- month post-operative intervals	Continuous	The PFDI-SF UDI scale will be computed at 6 month post-operative intervals using standard scoring algorithms described by Barber (2006) to create a measure scaled 0 to 100 at each time point. If data at any month are missing, the outcome variable will be coded as missing for that month. All longitudinal analyses or time-specific analyses will use all available data.
Incontinence severity at 6- month post-operative intervals as measures by the Hunskaar Incontinence Severity Index	Ordinal	The ISI scale will be computed at 6-month post operative intervals using the standardized scoring algorithm to generate an ordinal scale (no incontinence or incontinence levels of slight, moderate, severe, or very severe) as described by Sandvik (2000).
Risk of de novo voiding dysfunction defined at 6- month post-operative intervals (evaluated in aggregate fashion)	Binary	Defined as any incidence of a specific voiding dysfunction based on patient-supplied AE information. Rather than reporting data at six-month intervals, results will be aggregated across the follow-up period based on decision at masked review.

Variable	Туре	Definition
Risk of de novo incontinence defined at 6-month post- operative intervals (evaluated in aggregate fashion)	Binary	Defined as any incident case of new or worsening stress urinary incontinence or new or worsening urgency urinary incontinence as reported on either the Patient-reported AE forms or on the complication form obtained at six-month intervals. Based on masked data review, results will be aggregated across the reporting period rather than evaluated at six-month intervals

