9.4 Secondary Efficacy Analysis Methods

9.4.1 General Approach

As outlined in the above sections, the secondary outcome variables comprise a combination of binary, ordinal, and continuous measures that are collected at 6-month intervals through post-operative Month 24 and at either 6- or 12-month intervals thereafter. These outcome measures will be summarized in both tabular and graphical fashion by treatment arm over the full follow-up period, although the focus of the analysis will be on the first 36 months of the post-operative period. We will then use model-based approaches appropriate for the variable type (linear mixed models for continuous variables and GEE extensions of robust Poisson regression models for binary outcomes) to compare the outcomes for the two treatment arms across time.

Because the primary scientific interest for the study is in the trajectories of various the outcomes across time and because information about the patterns of these trajectories is limited, a longitudinal approach incorporating all time points will generally be employed. Specifically, the unit of analysis will be the participant visit, where visits are defined as in Section 4.5 starting 6 months post operatively, and the models will incorporate treatment group, time, and treatment group by time, as well as site, the randomization stratification variable, as fixed effects in the model with time (or visit) will be treated as a categorical variable to incorporate the expected non-linearity of time effects. Participant will be included as a random effect in the linear mixed model with an assumed compound symmetric covariance structure across the post-operative observation period and this same compound symmetric structure will be assumed in the GEE model with observations clustered within participant. The general structure of the SAS code that will be used for the mixed model (using the POPDI-6 as an example) is summarized below.

Proc Mixed data=SUPeR;

WHERE visit le 36; *** Constrains analysis to first 36 months of follow-up;
Class treatment visit center participant;
Model POPDI-6=treatment visit treatment*visit center/solution;
Random participant;
Lsmeans treatment*visit/ pdiff Cl;
Contrast 'POPDI Outcome' treatment 7 -7 treatment*month 111111111-1-1-1-1-1;

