10.2 Adverse Events

As described in Section 3.2, four types of measures will be utilized to characterize participant safety and tolerability measures. First, as a part of the inter-operative and peri-operative data collection forms, information will be collected on surgical complications that characterize the risk and tolerability of the procedure itself. Second, participants will be asked about specific targeted complications on both the post-operative visit and a standard study evaluation collected at 6-month intervals (with those complications automatically populating the AE form. Third, participants will be asked through a response to open-ended questions to report any post-surgery adverse events to the study coordinator or physician at the 6-week visit and at the subsequent follow-up visits at 6-month intervals. If a serious adverse event, particularly a hospitalization, occurs, the participants will be asked to report that immediately to the study coordinator or physician. All adverse events are captured by the study coordinator on the adverse event logs. Finally, specific pain information is being collected as a part of all follow-up visits to characterize differences in post-operative pain beyond 6 weeks.

The group of measures collected inter-operatively and peri-operatively includes those in the table below. These measures include continuous measures as well binary and ordinal measures. For the

continuous measures, summaries will be presented by treatment arm that include mean levels and standard deviations and linear models with treatment as the primary predictor, controlling for site will be used to test for differences by treatment arm. For the binary and ordinal measures, summaries will included counts and percentages associated with each level of the binary or ordinal measure and Cochran-Mantel-Haenszel statistics and associated p-value with analyses stratified by site will be used to characterize differences in the treatment arms.

The AEs collected through the standard AE form will be summarized using standard contingency tables by treatment arm. These summaries will be provided by individual treatment-emergent AEs, AEs by body system, and AEs by subject. In addition to these general descriptions, specific comparison of risk and differences across the treatment arms will be evaluated for the outcomes listed in the table below.

Summary of Safety V	ariables				
Inter-operative and peri-operative measures					
Variable	Туре	Definition			

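### The Incontinence Severity Index is kept as a five-level ordinal outcome, but the SAP summarises it by median and range and names no post-operative ordinal comparison, so a shift across levels can go unseen

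*SAP*

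**What the plan says.** SAP 9.2 types the Incontinence Severity Index as ordinal and says that the scoring will "generate an ordinal scale (no incontinence or incontinence levels of slight, moderate, severe, or very severe", which makes five levels at each visit. It is the only variable in the 9.2 table typed as ordinal. Protocol M.2 and SAP 3.2 both list it as a urinary outcome.

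The general rule for summaries in SAP 7.1 is that "ordinal data will be summarized by only presenting median and range".

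SAP 9.4.1 recognises that "the secondary outcome variables comprise a combination of binary, ordinal, and continuous measures". It also says "These outcome measures will be summarized in both tabular and graphical fashion by treatment arm over the full follow-up period" and promises models suited to the type of variable. The models it then lists are "linear mixed models for continuous variables and GEE extensions of robust Poisson regression models for binary outcomes". SAP 9.1 makes the same split: linear mixed models for continuous variables, and "binary outcome variables will be analyzed using robust Poisson regression models with a log link". SAP 9.4.3 describes the continuous and binary analyses in more detail and adds nothing for ordinal data.

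Ordinal methods appear in two other places. For baseline comparisons, SAP 7.2 gives the "Mantel-Haenszel mean score test using standardized midrank scores for ordinal measures". For inter- and peri-operative safety measures, SAP 10.2 says "summaries will included counts and percentages associated with each level of the binary or ordinal measure", with Cochran-Mantel-Haenszel statistics stratified by site.

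**The concern.** On a five-level scale, a median and a range carry little information. The median moves only when the 50% point crosses from one level to the next. The range depends on one woman at each end. Neither shows how many women sit at moderate or worse, which is what a reader wants to know about incontinence severity.

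The SAP therefore states a positive summary rule that discards the distribution, and no section names a test or model that would recover it after surgery. The index is listed in the attached baseline table, so the 7.2 midrank test applies to it there, where randomisation makes a difference uninteresting. After surgery, the analyst would have to choose between an ordinal model, a rank test, a dichotomy and a linear score without guidance.

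At stake is one secondary urinary outcome that Protocol M.2 assigns to the primary manuscript and says requires a statistical analysis plan.

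**Working it through.** There is no plan figure to reproduce: neither document gives a distribution, effect size or power for the index. The check has two parts.

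**1. Which rule reaches the post-operative index?**

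| SAP section | Applies to | Ordinal method |
|---|---|---|
| 7.1 | all summaries | median and range only |
| 7.2 | baseline comparisons | midrank mean score test |
| 9.1, 9.4.1, 9.4.3 | secondary efficacy | none named |
| 10.2 | inter- and peri-operative safety | n (%) per level, CMH by site |

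Only the 7.1 rule reaches it.

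**2. Can median and range hide a shift?**

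Assumptions: 80 women per arm at one visit (the SAP table shells show 88 and 87; 80 allows for some loss); a proportional-odds shift towards worse severity with common odds ratio 2; three assumed reference distributions.

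Formula: if C is the cumulative proportion at or below a level in the reference arm, the other arm has odds C/(1−C) divided by 2, and its cumulative proportion is odds/(1+odds).

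Reference distribution 45/25/18/9/3% (none to very severe):
- none: 0.45/0.55 = 0.818; ÷2 = 0.409; 0.409/1.409 = 0.29
- slight or better: 0.70/0.30 = 2.333; ÷2 = 1.167; 1.167/2.167 = 0.54
- moderate or better: 0.88/0.12 = 7.333; ÷2 = 3.667; 3.667/4.667 = 0.79

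Moderate or worse is 30% against 46%, and severe or worse is 12% against 21%. The 50% point lies in the slight level in both arms, so the true median is the same.

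In the other two distributions the true median does move:
- 35/28/22/11/4%: slight or better goes from 0.63 to 0.46 (1.703 ÷ 2 = 0.851; 0.851/1.851), so the median goes from slight to moderate.
- 60/20/12/6/2%: none goes from 0.60 to 0.43 (1.5 ÷ 2 = 0.75; 0.75/1.75), so the median goes from none to slight.

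Simulated results at odds ratio 2:

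| Reference, % none | Median and range identical | Identical, and rank test p<0.05 | Rank-test power |
|---|---|---|---|
| 45 | about 51% | about 24% | 0.67 |
| 35 | about 19–20% | about 5–6% | 0.69 |
| 60 | about 8% | about 1% | 0.63 |

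Sensitivity: with 88 and 87 women and four other assumed distributions (30%, 45%, 52% or 60% with no incontinence), median and range were identical in 64%, 11%, 44% and 54% of trials. They were identical with p<0.05 in 39%, 2%, 20% and 29%.

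A constructed example shows the mechanism. Take counts of 48/10/12/12/5 among 87 women and 66/12/5/3/2 among 88. Both arms have median none and the full range. Moderate or worse is 29/87 = 33.3% against 10/88 = 11.4%, and the rank test gives p = 0.0017.

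The summary can also mislead the other way. In the 45% distribution with no true difference, the sample medians differed in about 36% of trials.

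**The case against.** The case against rests on four points.

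- **An arm comparison is intended.** SAP 7.1 governs summaries, not tests. SAP 9.4.1 promises tables, graphs and models suited to the variable type, and Protocol section O promises appropriate parametric or nonparametric tests. SAP 16 leaves display shells to each manuscript. This stands: it would be wrong to infer that no comparison is meant. But no ordinal method is named, and Protocol section O defers the approach to the SAP.
- **The consequence is small.** SAP 7.7 calls secondary analyses exploratory and 9.4.3 calls them descriptive. The UDI-6 (continuous, modelled longitudinally) and new or worsening stress or urgency incontinence (binary) also cover continence. This stands in full.
- **SAP 10.2 does not contradict 7.1.** A reader might see a conflict between the two. The documents support only a general default beside a specific rule for inter- and peri-operative measures, which is ordinary drafting. SAP 10.2 matters here as evidence that the better summary is already in use.
- **Masking is far from certain.** A reader might infer that median and range will usually match on a five-level scale. The simulations do not support that. At an odds ratio of 2 they match in about half of trials in one of the three distributions and in a fifth or fewer in the other two.

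A reader might also infer a loss of power from cutting the index to any versus none. The SAP does not plan that cut. It dichotomises the PGI-I explicitly in 9.2 but keeps all five levels of the index, so such a loss cannot be charged to the plan.

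**Conclusion.** The concern holds as a specification gap with a weak summary rule. Followed as written, the SAP reports the post-operative index in a form that can hide a real shift across levels, and it names no ordinal analysis that would show one.

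Under the three main assumed distributions, with 80 women per arm and a common odds ratio of 2, median and range coincide in about 8% to 51% of trials, and coincide despite a rank-test p<0.05 in about 1% to 24%. The sensitivity set raises the upper ends to 64% and 39%. These figures depend on assumed distributions, above all on how close the 50% point lies to a boundary between levels. They show what can happen and do not predict this trial's data. The gap itself rests on the text alone.

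The reach is limited to one exploratory outcome. The primary outcome is unaffected. The change is worth making because the existing rule discards information already collected and the remedy is nearly free.

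**What to change.** 1. **SAP 7.1:** summarise ordinal outcomes by n (%) at each level, plus the median, by arm and visit, as 10.2 already does by level for peri-operative ordinal measures.
2. **SAP 9.4.1:** name one ordinal comparison of the index by visit. Either of these would do:
   - the midrank mean score test from 7.2, stratified by site, which needs no proportional-odds assumption; or
   - a cumulative-logit GEE with treatment, visit, treatment by visit and site, reporting the common odds ratio with its 95% interval at each visit. The baseline index is already collected and may be added, though the other 9.4.1 models carry no baseline term. State the working correlation and include a check of proportional odds.

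Fix the choice before the index is examined by arm. If it has already been examined, label the analysis as added afterwards.

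The cost is wording in two sections and a minor extra analysis, with no new data. If the model is chosen, it also brings the proportional-odds assumption.
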